12.3 Methods for Evaluation of Measurable Disease

All measurements should be taken and recorded in metric notation using a ruler or calipers. All baseline evaluations should be performed as closely as possible to the beginning of treatment and never more than 4 weeks before the beginning of the treatment.

The same method of assessment and the same technique should be used to characterize each identified and reported lesion at baseline and during follow-up. Imaging-based evaluation is preferred to evaluation by clinical examination unless the lesion(s) being followed cannot be imaged but are assessable by clinical exam.

Clinical lesions: Clinical lesions will only be considered measurable when they are superficial (e.g., skin nodules and palpable lymph nodes) and ≥ 10 mm diameter as assessed using calipers (e.g., skin nodules). In the case of skin lesions, documentation by color photography, including a ruler to estimate the size of the lesion, is recommended.

Chest x-ray: Lesions on chest x-ray are acceptable as measurable lesions when they are clearly defined and surrounded by aerated lung. However, CT is preferable.

Conventional CT and MRI: This guideline has defined measurability of lesions on CT scan based on the assumption that CT slice thickness is 5 mm or less. If CT scans have slice thickness greater than 5 mm, the minimum size for a measurable lesion should be twice the slice thickness. MRI is also acceptable in certain situations (e.g. for body scans).

Use of MRI remains a complex issue. MRI has excellent contrast, spatial, and temporal resolution; however, there are many image acquisition variables involved in MRI, which greatly impact image quality, lesion conspicuity, and measurement. Furthermore, the availability of MRI is variable globally. As with CT, if an MRI is performed, the technical specifications of the scanning sequences used should be optimized for the evaluation of the type and site of disease. Furthermore, as with CT, the modality used at follow-up should be the same as was used at baseline and the lesions should be measured/assessed on the same pulse sequence. It is beyond the scope of the RECIST guidelines to prescribe specific MRI pulse sequence parameters for all scanners, body parts, and diseases. Ideally, the same type of scanner should be used and the image acquisition protocol should be followed as closely as possible to prior scans. Body scans should be performed with breath-hold scanning techniques, if possible.

PET-CT: At present, the low dose or attenuation correction CT portion of a combined PET-CT is not always of optimal diagnostic CT quality for use with RECIST measurements. However, if the site can document that the CT performed as part of a PET-CT is of identical diagnostic quality to a diagnostic CT (with IV and oral contrast), then the CT portion of the PET-CT can be used for RECIST measurements and can be used interchangeably with conventional CT in accurately measuring cancer lesions over time. Note, however, that the PET portion of the CT introduces additional data which may bias an investigator if it is not routinely or serially performed.

Ultrasound: Ultrasound is not useful in assessment of lesion size and should not be used as a method of measurement. Ultrasound examinations cannot be reproduced in their entirety for independent review at a later date and, because they are operator dependent, it cannot be guaranteed that the same technique and measurements will be taken from one assessment to the next. If new lesions are identified by ultrasound in the course of the

study, confirmation by CT or MRI is advised. If there is concern about radiation exposure at CT, MRI may be used instead of CT in selected instances.

Endoscopy, Laparoscopy: The utilization of these techniques for objective tumor evaluation is not advised. However, such techniques may be useful to confirm complete pathological response when biopsies are obtained or to determine relapse in trials where recurrence following complete response (CR) or surgical resection is an endpoint.

Tumor markers: Tumor markers alone cannot be used to assess response. If markers are initially above the upper normal limit, they must normalize for a patient to be considered in complete clinical response.

Cytology, Histology: These techniques can be used to differentiate between partial responses (PR) and complete responses (CR) in rare cases (e.g., residual lesions in tumor types, such as germ cell tumors, where known residual benign tumors can remain).

The cytological confirmation of the neoplastic origin of any effusion that appears or worsens during treatment when the measurable tumor has met criteria for response or stable disease is mandatory to differentiate between response or stable disease (an effusion may be a side effect of the treatment) and progressive disease.

FDG-PET: While FDG-PET response assessments need additional study, it is sometimes reasonable to incorporate the use of FDG-PET scanning to complement CT scanning in assessment of progression (particularly possible 'new' disease). New lesions on the basis of FDG-PET imaging can be identified according to the following algorithm:

- Negative FDG-PET at baseline, with a positive FDG-PET at follow-up is a sign of PD based on a new lesion.
- No FDG-PET at baseline and a positive FDG-PET at follow-up: If the positive FDG-PET at follow-up corresponds to a new site of disease confirmed by CT, this is PD. If the positive FDG-PET at follow-up is not confirmed as a new site of disease on CT, additional follow-up CT scans are needed to determine if there is truly progression occurring at that site (if so, the date of PD will be the date of the initial abnormal FDG-PET scan). If the positive FDG-PET at follow-up corresponds to a pre-existing site of disease on CT that is not progressing on the basis of the anatomic images, this is not PD.
- FDG-PET may be used to upgrade a response to a CR in a manner similar to a biopsy in cases where a residual radiographic abnormality is thought to represent fibrosis or scarring. The use of FDG-PET in this circumstance should be prospectively described in the protocol and supported by disease-specific medical literature for the indication. However, it must be acknowledged that both approaches may lead to false positive CR due to limitations of FDG-PET and biopsy resolution/sensitivity.

Note: A 'positive' FDG-PET scan lesion means one which is FDG avid with an uptake greater than twice that of the surrounding tissue on the attenuation corrected image.

12.4 Response Criteria

12.4.1 Evaluation of Target Lesions

Complete Response (CR): Disappearance of all target lesions. Any pathological lymph nodes (whether target or non-target) must have reduction in short axis to <10 mm.

Partial Response (PR): At least a 30% decrease in the sum of the diameters of target lesions, taking as reference the baseline sum diameters.

Progressive Disease (PD): At least a 20% increase in the sum of the diameters of target lesions, taking as reference the smallest sum on study (this includes the baseline sum if that is the smallest on study). In addition to the relative increase of 20%, the sum must also demonstrate an absolute increase of at least 5 mm. (Note: the appearance of one or more new lesions is also considered progressions).

Stable Disease (SD): Neither sufficient shrinkage to qualify for PR nor sufficient increase to qualify for PD, taking as reference the smallest sum diameters while on study.

12.4.2 Evaluation of Non-Target Lesions

Complete Response (CR): Disappearance of all non-target lesions and normalization of tumor marker level. All lymph nodes must be non-pathological in size (<10 mm short axis).

Note: If tumor markers are initially above the upper normal limit, they must normalize for a patient to be considered in complete clinical response.

Non-CR/Non-PD: Persistence of one or more non-target lesion(s) and/or maintenance of tumor marker level above the normal limits.

Progressive Disease (PD): Appearance of one or more new lesions and/or unequivocal progression of existing non-target lesions. Unequivocal progression should not normally trump target lesion status. It must be representative of overall disease status change, not a single lesion increase.

Although a clear progression of “non-target” lesions only is exceptional, the opinion of the treating physician should prevail in such circumstances, and the progression status should be confirmed at a later time by the review panel (or Principal Investigator).

12.4.3 Evaluation of Best Overall Response

The best overall response is the best response recorded from the start of the treatment until disease progression/recurrence (taking as reference for progressive disease the smallest measurements recorded since the treatment started). The patient's best response assignment will depend on the achievement of both measurement and confirmation criteria.

For Patients with Measurable Disease (i.e., Target Disease)

Target Lesions	Non-Target Lesions	New Lesions	Overall Response	Best Overall Response when Confirmation is Required*
CR	CR	No	CR	>4 wks. Confirmation**
CR	Non-CR/Non-PD	No	PR	>4 wks. Confirmation**
CR	Not evaluated	No	PR	
PR	Non-CR/Non-PD/not evaluated	No	PR	
SD	Non-CR/Non-PD/not evaluated	No	SD	Documented at least once >4 wks. from baseline**
PD	Any	Yes or No	PD	no prior SD, PR or CR
Any	PD***	Yes or No	PD	
Any	Any	Yes	PD	

* See RECIST 1.1 manuscript for further details on what is evidence of a new lesion. ** Only for non-randomized trials with response as primary endpoint. *** In exceptional circumstances, unequivocal progression in non-target lesions may be accepted as disease progression. Note: Patients with a global deterioration of health status requiring discontinuation of treatment without objective evidence of disease progression at that time should be reported as “symptomatic deterioration.” Every effort should be made to document the objective progression even after discontinuation of treatment.
				

For Patients with Non-Measurable Disease (i.e., Non-Target Disease)

Non-Target Lesions	New Lesions	Overall Response
CR	No	CR
Non-CR/non-PD	No	Non-CR/non-PD*
Not all evaluated	No	not evaluated
Unequivocal PD	Yes or No	PD
Any	Yes	PD

* ‘Non-CR/non-PD’ is preferred over ‘stable disease’ for non-target disease since SD is increasingly used as an endpoint for assessment of efficacy in some trials so to assign this category when no lesions can be measured is not advised
		

12.4.4 Duration of Response

Duration of overall response: The duration of overall response is measured from the time measurement criteria are met for CR or PR (whichever is first recorded) until the first date that recurrent or progressive disease is objectively documented (taking as reference for progressive disease the smallest measurements recorded since the treatment started).

The duration of overall CR is measured from the time measurement criteria are first met for CR until the first date that progressive disease is objectively documented.

Duration of stable disease: Stable disease is measured from the start of the treatment until the criteria for progression are met, taking as reference the smallest measurements recorded since the treatment started, including the baseline measurements.

12.4.5 Progression-Free Survival

PFS is defined as the duration of time from start of treatment to time of progression or death, whichever occurs first.

12.4.6 Response Review

It is strongly recommended that all responses be reviewed by an expert(s) independent of the study at the study's completion.

13.0 DATA AND SAFETY MONITORING

In compliance with the Washington University Institutional Data and Safety Monitoring Plan, an independent Data and Safety Monitoring Committee (DSMC) will be specifically convened for this trial to review toxicity data at least every 6 months following the activation of the first secondary site. A DSMC will consist of no fewer than 3 members including 2 clinical investigators and a biostatistician. Like investigators, DSMC members are subject to the Washington University School of Medicine policies regarding standards of conduct. Individuals invited to serve on the DSMC will disclose any potential conflicts of interest to the trial principal investigator and/or appropriate university officials, in accordance with institution policies. Potential conflicts that develop during a trial or a member's tenure on a DSMC must also be disclosed.

The Data and Safety Monitoring (DSM) report will be prepared by the study statistician with assistance from the study team, will be reviewed by the DSMC, and will be submitted to the Washington University Quality Assurance and Safety Monitoring Committee (QASMC). This report will include:

- HRPO protocol number, protocol title, Principal Investigator name, data coordinator name, regulatory coordinator name, and statistician

- Date of initial HRPO approval, date of most recent consent HRPO approval/revision, date of HRPO expiration, date of most recent QA audit, study status, and phase of study
- History of study including summary of substantive amendments; summary of accrual suspensions including start/stop dates and reason; and summary of protocol exceptions, error, or breach of confidentiality including start/stop dates and reason
- Study-wide target accrual and study-wide actual accrual including numbers from participating sites
- Protocol activation date at each participating site
- Average rate of accrual observed in year 1, year 2, and subsequent years at each participating site
- Expected accrual end date and accrual by site
- Objectives of protocol with supporting data and list the number of participants who have met each objective
- Measures of efficacy
- Early stopping rules with supporting data and list the number of participants who have met the early stopping rules
- Summary of toxicities at all participating sites
- Abstract submissions/publications
- Summary of any recent literature that may affect the safety or ethics of the study

Further DSMC responsibilities are described in the DSMC charter.

Until such a time as the first secondary site activates this protocol, a semi-annual DSM report to be prepared by the study team will be submitted to the QASM Committee beginning 6 months after study activation at Washington University.

The study principal investigator and coordinator will monitor for serious toxicities on an ongoing basis. Once the principal investigator or coordinator becomes aware of an adverse event, the AE will be reported to the HRPO and QASMC according to institutional guidelines (please refer to Section 7.0).

Refer to the Washington University Quality Assurance and Data Safety Monitoring Committee Policies and Procedures for full details on the responsibilities of the DSMC at <https://siteman.wustl.edu/wp-content/uploads/2015/10/QASMC-Policies-and-Procedures-03.31.2015.pdf>

14.0 AUDITING

As coordinating center of this trial, Washington University (via the Quality Assurance and Safety Monitoring Committee (QASMC)) will monitor each participating site to ensure that all protocol requirements are being met; that applicable federal regulations are being followed; and that best practices for patient safety and data collection are being followed per protocol. Participating sites will be asked to send copies of all audit materials, including source documentation. The audit notification will be sent to the Washington University Research Patient Coordinator, who will obtain the audit materials from the participating institution.

Notification of an upcoming audit will be sent to the research team one month ahead of the audit. Once accrual numbers are confirmed, and approximately 30 days prior to the audit, a list of the cases selected for review (up to 10 for each site) will be sent to the research team. However, if during the audit the need arises to review cases not initially selected, the research team will be asked to provide the additional charts within two working days.

Items to be evaluated include:

- Subject screening and enrollment
- Reporting of adverse events
- Maintenance of HIPAA compliance
- Completeness of regulatory documentation
- Completeness of participant documentation
- Acquisition of informed consent
- IRB documentation
- Issues of protocol adherence

Additional details regarding the auditing policies and procedures can be found at <https://siteman.wustl.edu/wp-content/uploads/2015/10/QASMC-Policies-and-Procedures-03.31.2015.pdf>

15.0 STATISTICAL CONSIDERATIONS

15.1 Study Description

This is a single arm phase II clinical trial with metastatic HR+ HER2- breast cancer patients treated by palbociclib on a 5 days on/2 days off schedule.

The primary endpoint of the trial is the rate of grade 3 or higher adverse events (AE rate) within the first 29 days (equivalently, 1-AE rate, i.e., the proportion of patients not suffering grade 3 or 4 AEs) The secondary endpoints include AE rate in all cycles, rate of palbociclib dose reduction or interruption or discontinuation, AE profiles, PFS, ORR, and clinical benefit rate.

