A randomized phase 3 study to confirm the efficacy of palbociclib in combination with letrozole in this setting (PALOMA2) was recently reported at ASCO 2016 annual meeting and again demonstrated a significant improvement in progression free survival (PFS): 24.8 (22.1-NR) months in the palbociclib/letrozole arm vs 14.5 (12.9-17.1) months in the placebo/letrozole arm, HR 0.58; $p < 0.000001$ (12). Among the 444 patients treated with palbociclib and letrozole, neutropenia (any grade) occurred in 80% of patients vs. 6% in the placebo/letrozole arm. The incidence of grade 3 and 4 neutropenia in the palbociclib/letrozole arm was 56% and 10%, respectively. Grade 3 or 4 non-hematological AEs were uncommon. 9.7% of patients in the palbociclib/letrozole arm vs 5.9% in the placebo/letrozole arm discontinued treatment due to AEs (12).

Most recently, a randomized phase 3 study (PALOMA3) assessed the safety and efficacy of the combination of palbociclib and fulvestrant vs placebo and fulvestrant after disease progression after prior endocrine therapy in premenopausal and postmenopausal women with hormone receptor positive and Her-2/neu negative advanced breast cancer. In this study, premenopausal females also received goserelin for ovarian suppression. A significantly prolonged PFS was noted with the combination of palbociclib and fulvestrant compared with fulvestrant and placebo. The dosing schedule of palbociclib was 125 mg po daily for 3 weeks followed by one week off drug (13).

Similar to PALOMA2, most common hematologic adverse events reported for the palbociclib–fulvestrant group in PALOMA3 were neutropenia and leukopenia. Neutropenia (any grade) occurred in 78.8% of the patients receiving palbociclib–fulvestrant versus 3.5% in the placebo–fulvestrant group, leukopenia in 45.5% versus 4.1%, anemia in 26.1% versus 9.9%, and thrombocytopenia in 19.4% versus 0%. Grade 3 or 4 neutropenia occurred in 62.0% of the patients receiving palbociclib–fulvestrant versus 0.6% of the patients receiving placebo–fulvestrant, leukopenia in 25.2% versus 0.6%, anemia in 2.6% versus 1.7%, and thrombocytopenia in 2.3% versus 0%. The most common nonhematologic adverse events were fatigue, nausea (29.0% vs. 26.2%), and headache, all of which were more common in the palbociclib-fulvestrant group. A higher incidence of infections was also reported in the palbociclib–fulvestrant group (13).

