2.0 OBJECTIVES

2.1 Primary Objective

To determine the rate of grade 3 or higher neutropenia in patients with hormone receptor positive breast cancer treated with palbociclib on a 5 days on/2 days off schedule within the first 29 days of treatment.

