15.2 Sample Size Calculations

The rate of grade 3 or higher neutropenia in PALOMA -1 and PALOMA – 3 was 54% and 62% respectively. We anticipate the new schedule to have less toxicity leading to around 40%-50% AE rate. The sample size was calculated to test the one-sided null hypothesis that 1-AE (adverse event) rate ≤ 0.38 (i.e., AE rate >0.62) versus the alternative that 1-AE rate ≥ 0.6 (i.e., AE rate <0.4). Enrollment of 47 patients will be required to achieve 90% power (actual power=91.8%) based on one-sample binomial exact test at a 5% level (actual alpha=4.7%). If no grade 3 or higher adverse events were observed on 24 or more patients on the alternative dosing schedule, the alternative dosing will be deemed to show better toxicity profile than standard schedule.

The CBR was estimated as 84.3% (80%~88%) in 1st line and 67% from PALOMA-3 in 2nd line patients. With an estimation that 70% of the enrolled patients are 2nd line, we expect approximately 33 2nd line patients and 14 1st line patients and thus ~22 2nd line patients with ~11 1st line patients with clinical benefit. With 33 2nd line patients, the CBR can be estimated with a 95% two-sided Clopper-Pearson exact CI of 48.5~82.3% given the true CBR is 67% as in PALOMA-3 while the CBR in the 14 1st line patients can be estimated with a 95% CI of 55.5%~97.7% given the true CBR is 84.3%.

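### The primary test counts any grade 3 or higher adverse event, but the primary objective and the 62% null rate are grade 3 or higher neutropenia

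*Combined protocol and SAP*

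**What the plan says.** The primary objective in Section 2.1 is "To determine the rate of grade 3 or higher neutropenia in patients with hormone receptor positive breast cancer treated with palbociclib" on the new schedule, within the first 29 days.

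Section 15.1 words the endpoint differently: "The primary endpoint of the trial is the rate of grade 3 or higher adverse events (AE rate) within the first 29 days". It also gives the complement, "the proportion of patients not suffering grade 3 or 4 AEs".

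Section 15.2 starts from neutropenia: "The rate of grade 3 or higher neutropenia in PALOMA -1 and PALOMA – 3 was 54% and 62% respectively". It anticipates a 40% to 50% AE rate on the new schedule. It tests a null AE rate of 62% (event-free proportion 0.38) against an alternative of 40% (event-free proportion 0.60), using a one-sided exact binomial test in 47 patients. The success condition reads: "If no grade 3 or higher adverse events were observed on 24 or more patients on the alternative dosing schedule".

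Section 1.2 confirms what the 62% is: "Grade 3 or 4 neutropenia occurred in 62.0% of the patients receiving" palbociclib with fulvestrant in PALOMA-3. AE is expanded in Section 15.2 only as adverse event, and Section 7.1.1 defines an adverse event as any unfavorable medical occurrence.

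**The concern.** The objective and the null rate refer to neutropenia, while the named endpoint and the success rule refer to every grade 3 or higher adverse event. Under the rule as written, a patient with grade 3 fatigue, infection, anemia or a disease-related event, and no neutropenia, counts against the new schedule. The 62% benchmark never counted such patients.

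Any grade 3 or higher adverse event is at least as frequent as grade 3 or higher neutropenia, so the mismatch works in one direction, against the new schedule. This is the trial's only formal hypothesis test. An analyst following Section 2.1 and one following Section 15 would count different patients, both could claim to follow the protocol, and the choice could be made after the data are seen.

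**Working it through.** **Inputs.** From Section 15.2: n = 47, cut-off 24 event-free patients, event-free proportion 0.38 under the null and 0.60 under the alternative, one-sided exact binomial test. From Sections 1.2 and 15.2: the 62% is a neutropenia rate. Assumed: q, the share of patients free of grade 3 or higher neutropenia who have some other grade 3 or higher adverse event by day 29. The documents give no value for q, so a range is shown.

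**Step 1: the plan's own figures.** With X the number of event-free patients out of 47:

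- Alpha = P(X ≥ 24 | p = 0.38) = 0.0466 (stated 4.7%).
- Power = P(X ≥ 24 | p = 0.60) = 0.9181 (stated 91.8%).
- 47 is the smallest n with exact alpha of at most 5% and power of at least 90%.

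The arithmetic is right. The question is which event is counted.

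**Step 2: the literal rule.** A patient counts as a success only if free of neutropenia and of every other grade 3 or higher event. The success probability is therefore

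p(q) = (1 − neutropenia rate) × (1 − q),

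and the chance of passing is P(X ≥ 24 | p(q)). For example, at 40% neutropenia and q = 10%, p = 0.60 × 0.90 = 0.54.

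| q (assumed) | p at 40% neutropenia | Chance of passing | p at 62% neutropenia | Chance of passing |
|---|---|---|---|---|
| 0 | 0.600 | 91.8% | 0.380 | 4.7% |
| 3% | 0.582 | 87.2% | 0.369 | 3.3% |
| 5% | 0.570 | 83.4% | 0.361 | 2.5% |
| 10% | 0.540 | 71.0% | 0.342 | 1.3% |
| 15% | 0.510 | 55.5% | 0.323 | 0.6% |
| 20% | 0.480 | 39.1% | 0.304 | 0.2% |

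A value of q as small as 3% already takes power below the 90% target.

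**Step 3: can the two readings disagree in one data set?** Yes. If 26 of 47 patients have no grade 3 or higher neutropenia, the neutropenia rule passes (26 ≥ 24). If 3 of those 26 have another grade 3 or higher event, 26 − 3 = 23 remain and the literal rule fails.

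**Step 4: what the documents say about other events.** Section 1.2 reports grade 3 or 4 leukopenia in 25.2%, anemia in 2.6% and thrombocytopenia in 2.3% of the palbociclib–fulvestrant group in PALOMA-3. For PALOMA-2 it says that grade 3 or 4 non-hematological events were uncommon. The overlap with neutropenia is not given and none of these figures is tied to 29 days, so q cannot be derived from them.

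**The case against.** The best defence is that AE rate is shorthand for the neutropenia rate. Section 15.2 opens with neutropenia and carries the 62% straight into the null. The endpoint list in Section 15.1 follows the order of the objectives: AE rate in 29 days sits where the primary objective sits, AE rate in all cycles sits where secondary objective 1 (all-cycle neutropenia) sits, and AE profiles are listed separately. If AE rate meant any event, the neutropenia objectives would have no endpoint. On this reading the design is coherent.

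That is probably the intent, and it supports the proposed fix. It does not remove the defect, because no section states it, the general definition in Section 7.1.1 points the other way, and the success rule itself is written in terms of adverse events.

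Four narrower points stand:

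- The literal rule is conservative: it lowers the chance of a false pass on neutropenia. Disagreement runs one way only, passing on neutropenia and failing on any event.
- The power loss depends on q, which the documents do not give. At low q it is a reduction in power, not a collapse.
- The 40% to 50% expectation is the authors' own figure with no source. Only the 54% and 62% are labelled as neutropenia.
- The all-cycle secondary endpoint has no null rate or success rule, so the mismatch there is one of label.

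**Conclusion.** The concern holds, and the plan is wrong as written: the rule for the primary hypothesis counts a broader event than the objective and the null rate it is tested against. If true neutropenia is 40% and the rule is applied literally, power falls from 91.8% to 83.4%, 71.0% or 39.1% for q of 5%, 10% or 20%. At 62% neutropenia the chance of passing falls from 4.7% to 2.5%, 1.3% or 0.2%. The direction is certain, because a broader event cannot be rarer. The size is conditional on q, which is assumed. The stake is wrongly failing a schedule that meets the design alternative, together with a primary endpoint open to two readings. This must be fixed before analysis.

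**What to change.** In Section 15.1, define the primary endpoint as the proportion of patients with grade 3 or higher neutropenia (CTCAE v4.0, ANC below 1,000/mcL) within the first 29 days, and its complement as the proportion without it. Use the same event for the all-cycle secondary endpoint. In Section 15.2, restate the hypotheses as neutropenia rates and the rule as no grade 3 or higher neutropenia in 24 or more of 47 patients. In Section 15.3, replace AE rate with the neutropenia rate. Report any grade 3 or higher adverse event descriptively under secondary objective 3.

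The cost is a wording amendment. With neutropenia as the event, n = 47, the cut-off of 24, alpha 4.7% and power 91.8% all stand, and data collection does not change.

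If any grade 3 or higher adverse event is what the sponsor intends, Section 2.1 must change and the null needs an any-event benchmark, which the documents do not contain. The sample size would then have to be recalculated.
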